11.6.2 Secondary endpoint analysis

Bailey Scales of Infant Development III at 12 and 24 months: Differences in the scores of psychomotor development and neurocognitive development, respectively, between the groups will be analyzed by repeated measures ANOVA, also accounting for confounders (e.g. birth weight, IVH Grade 3/4, cystic periventricular leucomalacia, NEC). In case of twins, the analysis will be carried out 1) as mention above, but only including the firstborn and 2) by calculating a mixed model with mother and child as random factor. In case of too many drop outs, descriptive statistics will be carried out.

For Gross Motor function measurements at 12 and 24 months, descriptive statistics will be conducted.

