2. PROTOCOL SYNOPSIS

TITLE	Preventing Cholestasis in Premature Infants Using SMOFLipid®					
OBJECTIVES	
Primary Objective
 
 To compare a mixed parenteral lipid emulsion containing fish oil (SMOFLipid®) with a soybean oil based lipid emulsion (Intralipid®) for its effect on the occurrence of parenteral nutrition associated cholestasis in extremely low birth weight infants 
Secondary Objectives
 
 To assess the impact of SMOFLipid® on the long term neurocognitive development of extreme low birth weight infants at 12 and 24 months of corrected age 					
DESIGN / PHASE	Prospective, randomized, double-blind, phase IV study.					
STUDY PLANNED DURATION	First patient First visit	1st month	Last patient First visit	36 month s	Last patient Last visit	62 months
CENTER(S) / COUNTRY(IES)	Single center, Austria (Medical University Vienna, Austria; Department of Neonatology, Pediatric Intensive Care and Neuropediatrics, University Children's Hospital,)					
PATIENTS / GROUPS	
200 patients in 2 groups 100 patients per group Block randomization ratio 1:1, stratification by sex and weight (in two groups: < 750 gram vs. ≥750 gram).
 
In case of twins, randomization will be applied to the firstborn; the twin will be assigned to the other treatment group. Triplets or higher will be excluded.
					
INCLUSION CRITERIA	
 Infants born with a birth weight ≤ 1000 Gram (= extreme low birth weight infants) Admission to the neonatal ward in the first 24 hours of life Informed consent obtained and randomized on study drug the first 5 days of life 					
EXCLUSION CRITERIA	
 Triplets or higher Conjugated bilirubin > 1.5 mg/dl before inclusion to the study Conditions associated with cholestasis independent of parenteral nutrition: 
 Inborn errors of metabolism Viral Infections (cytomegaly virus, HIV, Hepatitis B, C) Immune mediated hemolytic disease (e.g. Rhesus incompatibility) Cystic fibrosis Primary cholestatic diseases of the liver For Neurodevelopmental outcome in follow up phase: Congenital neurological malformations and chromosomal aberrations 					

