6.2 Secondary Objectives

To investigate whether ELBW infants treated with two different ILEs (investigational drug: SMOFLipid®, comparative drug: Intralipid®) differ in their neurodevelopment (Bailey Scales of Infant Development III) at 12 and 24 months of corrected gestational age

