7. STUDY DESIGN

7.1 Study population

7.1.1 Subject population

Population: Extreme low birth weight (ELBW) infants

Recruitment: About 90 ELBW infants are admitted to our unit each year in the first 24 hours of life.

We expect to recruit 90 % (81 patients/a year) to the study.

Drop Outs: Based on a mortality of 22% in 2010 ([name], unpublished data) and a conservative calculation, we expect 18/81 patients to drop out, leaving 63 patients a year for analysis of the primary outcome. We do not expect any other reasons for drop out.

Losses to follow up: 63 patients are expected to be discharged from hospital each year. Based on a follow up rate of 60% after discharge in 2009 ([name], unpublished data), we expect about 38/63 patients to be available for analysis of the secondary outcome each year. In the end we expect to lose 80/200 patients to follow up.

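### The only secondary objective (Bayley III at 12 and 24 months) falls back to description at an undefined level of drop-out, although 40% loss is already expected, and its lead analysis may discard infants seen once

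*Combined protocol and SAP*

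**What the plan says.** Section 6.2 sets one secondary objective: whether the two groups "differ in their neurodevelopment (Bailey Scales of Infant Development III) at 12 and 24 months of corrected gestational age". The synopsis likewise lists a single secondary objective.

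Section 11.6.2 says that differences in the scores "between the groups will be analyzed by repeated measures ANOVA, also accounting for confounders". Where there are twins, it asks for two analyses: the same one restricted to firstborns, and a second "by calculating a mixed model with mother and child as random factor". It then adds: "In case of too many drop outs, descriptive statistics will be carried out". The statistical methodology part of the synopsis carries the same fallback.

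Section 7.1.1 forecasts the loss. "Based on a follow up rate of 60% after discharge in 2009", it expects about 38 of 63 discharged infants a year to be available for the secondary outcome, and concludes: "In the end we expect to lose 80/200 patients to follow up".

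Section 11.5, on missing data, deals with blood samples and withdrawal before week 18. It has no rule for missing developmental scores. Section 11.4 defers full detail to an SAP, but no threshold for drop-out appears in the documents.

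**The concern.** The fallback turns on a quantity that the plan never defines, while the plan's own base case is a 40% loss. A reader cannot tell whether 40% already counts as too many, and so whether the secondary hypothesis will be tested at all. If the fallback is used, the trial has no inferential result on neurodevelopment, the one question it follows infants to 24 months to answer.

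The lead method adds to this. A classical repeated measures ANOVA needs both scores and by default leaves out an infant who attended only one visit. With losses this heavy, that could remove a substantial share of the infants who were assessed, and those who remain may be a selected group.

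**Working it through.** **1. The plan's forecast.** Inputs from section 7.1.1: 60% follow-up, 63 discharged a year, base of 200.
- 200 × (1 − 0.60) = 80, and 80/200 = 40%. The stated figure reproduces.
- 63 × 0.60 = 37.8, about 38 a year; 1 − 38/63 = 39.7%.
- Of the 81 recruited a year, 38/81 = 47% would have the secondary outcome.

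**2. What is left per arm.**
- From the base of 200: 120/2 = 60.
- From the yearly forecast over three years: 38 × 3 = 114, and 114/2 = 57.
- From the planned 122 per group (section 11.2): 122 × 0.78 × 0.60 = 57.1.

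**3. Detectable difference.** The documents give no SD or target difference for the Bayley III, so I work in SD units for a single-visit comparison with two-sided alpha 0.05 and 80% power: d = (1.96 + 0.8416) × √(2/n).
- n = 60: 0.51 SD. n = 57: 0.52 SD. For reference, n = 100: 0.40 SD.
- Power at 60 per arm is 45%, 59% and 78% for true differences of 0.33, 0.40 and 0.50 SD.

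**4. What deleting single-visit infants could cost.** The documents do not give joint attendance at the two visits. Assumptions: 60% attend each visit, the correlation between the two scores is ρ = 0.6, and the SD is 1. Let b be the share with both scores and s the share seen only at 24 months, with the same share seen only at 12 months. Variances of the 24-month mean are per infant eligible for follow-up:
- complete cases: 1/b
- all 24-month scores: 1/0.60 = 1.67
- likelihood model on all scores: A/(A² − C²), with A = b/(1 − ρ²) + s and C = ρb/(1 − ρ²)

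For b = 0.50, s = 0.10: A = 0.50/0.64 + 0.10 = 0.881, C = 0.6 × 0.50/0.64 = 0.469, and the variance is 0.881/(0.881² − 0.469²) = 1.58. The gain over complete cases is 2.00/1.58 − 1 = 26%.

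| Both / 24 only / 12 only / neither | Complete cases | Mixed model | Gain over complete cases | Gain over all 24-month scores |
|---|---|---|---|---|
| 60 / 0 / 0 / 40% | 1.67 | 1.67 | 0% | 0% |
| 50 / 10 / 10 / 30% | 2.00 | 1.58 | 26% | 5% |
| 45 / 15 / 15 / 25% | 2.22 | 1.55 | 43% | 7% |
| 36 / 24 / 24 / 16% (independent) | 2.78 | 1.51 | 83% | 10% |

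In the second and third rows complete-case analysis drops 20/70 = 29% and 30/75 = 40% of infants with at least one score. The standard error under the mixed model is 11% and 16% smaller (1 − √(1.58/2.00) and 1 − √(1.55/2.22)).

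The last column shows where the gain comes from. Most of it is the retention of infants seen only at 24 months; borrowing from the 12-month score adds little.

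**The case against.** Several stronger readings are tempting, and the documents do not support them.

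- **That a mixed model is planned only for twins.** Section 11.6.2 contrasts a firstborn-only analysis with a mixed model. The first most naturally means singletons plus firstborn twins, so the second is plausibly the whole cohort with second twins kept. The model is then already in the plan. What is missing is a statement that it leads, and that infants with one score enter it.
- **That the plan deletes infants with one score.** It does not say so. Deletion is the default of the classical method.
- **That the ANOVA is valid only if scores are missing completely at random.** Complete-case analysis adjusted for covariates also holds when missingness depends only on those covariates. The plan adjusts for birth weight, intraventricular haemorrhage, periventricular leucomalacia and necrotizing enterocolitis, which could well drive attendance.
- **That the test would be dropped after looking at the results.** The trigger is the number of drop-outs, not the scores, and section 8.3.2 keeps the follow-up assessors blinded. The same section does break the codes after the primary analysis, while follow-up runs to month 62, so nothing fixes the decision before unblinding. The text supports saying that threshold, time and decision-maker are absent, and no more.

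It is also fair to object that section 7.1.1 may mean the same 60% attend both visits, in which case the efficiency gain is nil. The endpoint is secondary and has no sample size calculation of its own, and the primary result is unaffected. All of this stands, but none of it supplies a rule for the fallback.

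**Conclusion.** The point holds. The fallback has no defined trigger, the expected loss is already 40%, and section 11.5 does not cover missing Bayley scores, so the plan does not guarantee any inferential answer to its only secondary objective. That conclusion rests on the text alone.

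The size of the efficiency loss is much less certain. It applies only if single-visit infants are in fact deleted, and it depends on the assumed joint attendance, the correlation of 0.6 and 60% attendance per visit. The full range of 0% to about 83% should be shown; the middle scenarios of 26% and 43% are illustrations, not estimates. With a detectable difference of about half an SD, a non-significant result would be weak evidence of no effect. That is a reason to report an estimate with its interval, not a reason to withhold the comparison.

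**What to change.** In section 11.6.2 and in the synopsis:

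- Delete the sentence on too many drop-outs.
- Make the likelihood-based mixed model with mother and child as random factors the leading analysis, for all infants with at least one Bayley III score.
- Include treatment, visit, treatment × visit, the stratification factors (sex and birth-weight group) and the baseline covariates already planned. The morbidities on the present list are recorded at discharge; state expressly whether they stay in the model, so that they are not lost by omission.
- Report the treatment contrast with its confidence interval at both 12 and 24 months, since section 6.2 names both ages.
- Always run the model, whatever the attrition, and report by arm how many infants have both scores, one score or none.

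The cost is a change of wording: the model is already named and SAS is already listed in section 11.8. The limit is that the model assumes scores are missing at random given what is in it, and it recovers nothing for infants with neither score (16 to 40% of those eligible in the scenarios above). The result should be reported with that stated.

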11.6.3 Safety and tolerability endpoints

Hypertriglyceridemia: Peak level in mg/dl

11.6.4 Baseline parameters and concomitant medications

The following parameters will be investigated:

Sex (m/f)

Age at birth (gestational weeks + days)

Twin (yes/no)

Mode of delivery (caesarean section/spontaneous delivery)

Received any prenatal steroids for lung maturation (yes/no).

Weight (gram) at birth

Length (cm) at birth

Head circumference (cm) at birth

Small for gestational age (< 10. percentile birth weight, yes/no)

Apgar scores at 1, 5 and 10 minutes (0-10)

Umbilical artery pH

Comcomitant medications and changes in concomitant medication will be documented by the Investigator.

11.7 Interim analysis

No interim analysis planned.

11.8 Software program(s)

SAS 9.2

Microsoft Excel

12.DOCUMENTATION AND DATA MANAGEMENT

12.1 Documentation of study results

A subject screening and enrollment Log will be completed for all eligible or non-eligible subjects with the reasons for exclusion.

12.1.1 Case report form (CRF)

For each subject enrolled, regardless of study drug initiation, a paper CRF must be completed and signed by the investigator or a designated sub-investigator. This also applies to those subjects who fail to complete the study. If a subject withdraws from the study, the reason must be noted on the CRF. Case report forms are to be completed on an ongoing basis.

CRF entries and corrections will only be performed by study site staff, authorized by the investigator. In a "Paper-CRF" all forms should be completed and must be legible. Errors should be crossed out but not obliterated, the correction inserted, and the change initialed and dated by the investigator, co-investigator or study nurse.

The entries will be checked by trained personnel (Monitor) and any errors or inconsistencies will be checked immediately.

The monitor will collect original completed and signed CRFs at the end of the study. A copy of the completed and signed CRFs will remain on site.

Completed CRFs will be passed to the Statistician for further analysis.

12.1.2 Data Collection

Data collected at all visits are entered into an interactive form. The CRFs will be source documents verified following guidelines established before study onset as detailed in the Monitoring Plan.

12.2 Safekeeping

The investigator will maintain adequate and accurate records to enable the conduct of the study to be fully documented and the study data to be subsequently verified (according to ICH-GCP “essential documents”). These documents will be classified into two different categories: investigator's file, and subject clinical source documents.

The investigator's file will contain the protocol/amendments, EudraCT forms, CRFs (eCRF printout), standard operation procedures (SOPs), data clarification and query forms, EC/IRB and Health Authority approval with correspondence, informed consent, drug records, staff curriculum vitae and authorization forms, screening and enrollment logs, and other appropriate documents/correspondence as per ICH/Good Clinical Practice (GCP) and local regulations.

Subject clinical source documents include, but are not limited to subject hospital/clinic records, physician's and nurse's notes, appointment book, original laboratory reports, ECG, X-ray, pathology and special assessment reports, consultant letters, etc.

These two categories of documents must be kept on file by the investigator for as long as needed to comply with national and international regulations (in Austria 15 years after discontinuing clinical development or after the last marketing approval). If source documents are not durable as long as needed (e.g. ECG printouts) they must be preserved as a copy. No study document should be destroyed without prior written approval from the Department of

When source documents are required for the continued care of the subject, appropriate copies should be made for storing outside of the site.

12.3 Quality Control and Quality Assurance

12.3.1 Periodic Monitoring

According to GCP at least 3 monitoring visits are scheduled. An initiation visit, one routine visit and a close out visit after the last patient has finished the study or data base lock.

The designated monitor will contact and visit the investigator regularly and will be allowed to have access to all source documents needed to verify the entries in the CRFs and other protocol-related documents provided that subject confidentiality is maintained in agreement with local regulations. It will be the monitor's responsibility to inspect the CRFs at regular intervals according to the monitoring plan throughout the study, to verify the adherence to the protocol and the completeness, consistency and accuracy of the data being entered on them. The monitoring standards require full verification for the presence of informed consent, adherence to the inclusion/exclusion criteria, documentation of SAEs and the recording of the main efficacy, safety, and tolerability endpoints. The monitor will be working according to SOPs and will provide a monitoring report after each visit for the Sponsor. Depending on the quality of the data, additional monitoring visits may be necessary according to the sponsor's discretion. The investigator will resolve discrepancies of data.

Monitoring will be performed by Koordinierungszentrum für Klinische Studien on a regular basis and will follow a detailed Monitoring Plan.

12.3.2 Audit and Inspections

Upon request, the investigator will make all study-related source data and records available to a qualified quality assurance auditor mandated by the sponsor or to competent authority inspectors. The main purposes of an audit or inspection are to confirm that the rights and welfare of the subjects have been adequately protected, and that all data relevant for assessment of safety and efficacy of the investigational product have appropriately been reported to the sponsor.

12.4 Reporting and Publication

12.4.1 Publication of study results

The findings of this study will be published by the sponsor (investigators) in a scientific journal and presented at scientific meetings. The manuscript will be circulated to all co-investigators before submission. Confidentiality of subjects in reports/publications will be guaranteed.

13. ETHICAL AND LEGAL ASPECTS

13.1 Informed consent of subjects

Following comprehensive instruction regarding the nature, significance, impact and risks of this clinical trial, a patient's caregiver (mother or father) must give written consent to participation in the study.

During the instruction the trial participants are to be made aware of the fact that they can withdraw their consent – without giving reasons – at any time without their further medical care being influenced in any way.

In addition to the comprehensive instructions given to the trial participants by the investigator, the trial participants also receive a written patient information sheet in comprehensible language, explaining the nature and purpose of the study and its progress.

The patients must agree to the possibility of study-related data being passed on to relevant authorities.

The patients must be informed in detail of their obligations in relation to the trial participants insurance in order not to jeopardize insurance cover.

13.2 Acknowledgement / approval of the study

The investigator (or a designated CRO) will submit this protocol and any related document provided to the subject (such as subject information used to obtain informed consent) to an Ethics Committee (EC) or Institutional Review Board (IRB). Approval from the committee must be obtained before starting the study.

The clinical trial shall be performed in full compliance with the legal regulations according to the Drug Law (AMG - Arzneimittelgesetz) of the Republic of Austria.

An application must also be submitted to the Austrian Competent Authorities (Bundesamt für Sicherheit im Gesundheitswesen (BASG) represented by the Agency for Health and Food Safety (AGES PharmMed) and registered to the European Clinical Trial Database (EudraCT) using the required forms. The timelines for (silent) approval set by national law must be followed before starting the study.

13.2.1 Changes in the Conduct of the Study

Protocol amendments

Proposed amendments must be submitted to the appropriate CA and ECs. Substantial amendments may be implemented only after CA/EC approval has been obtained. Amendments that are intended to eliminate an apparent immediate hazard to subjects may be implemented prior to receiving CA/EC approval. However, in this case, approval must be obtained as soon as possible after implementation.

Study Termination

If the sponsor or the investigator decides to terminate the study before it is completed, they will notify each other in writing stating the reasons of early termination. In terminating the study, the sponsor and the investigator will ensure the adequate consideration is given to the protection of the subject interests. The investigator, sponsor or (designated CRO on behalf of the sponsor) will notify the relevant CA and EC. Documentation will be filed in the Trial Master and Investigator Files.

Clinical Study Report (CSR)

Within one year after the final completion of the study, a full CSR will be prepared by the sponsor and submitted to the EC and the competent authority.

The Investigator will be asked to review and sign the final study report.

13.3 Insurance

During their participation in the clinical trial the patients will be insured as defined by legal requirements. The investigator of the clinical trial will receive a copy of the insurance conditions of the 'patients insurance'. The sponsor is providing insurance in order to indemnify (legal and financial coverage) the investigator/center against claims arising from the study, except for claims that arise from malpractice and/or negligence. The compensation of the subject in the event of study-related injuries will comply with the applicable regulations.

Details on the existing patients insurance are given in the patient information sheet.

Patients will be insured by the Zürich-Versicherung (Nr. 07229622-2) according to the Austrian law. Please indicate insurance details!

13.5 Ethics and Good Clinical Practice (GCP)

The investigator will ensure that this study is conducted in full conformance with the principles of the "Declaration of Helsinki" (as amended at the 56th WMA General Assembly, Tokyo, Japan, 2008) and with the laws and regulations of the country in which the clinical research is conducted.

The investigator of the clinical trial shall guarantee that only appropriately trained personnel will be involved in the study. All studies must follow the ICH GCP Guidelines (June 1996) and, if applicable, the Code of Federal Regulations (USA). In other countries in which GCP Guidelines exist, the investigators will strictly ensure adherence to the stated provisions.

Therefore this study follows the EU Directive embedded in the Austrian drug act.

